8. METHODS OF ASSESSMENT AND ENDPOINTS

All trial data during the dose-escalation stage (Stage 1) and expansion stage (Stage 2) will be recorded on the eCRFs. Timing of study procedures for the dose-escalation stage (Stage 1) and expansion stage (Stage 2) are listed in schedules of assessments tables – Table 8: Schedule of Assessments (LAM-002A Continuous Monotherapy Administration), Table 9: Schedule of Assessments (LAM-002A Intermittent Monotherapy Administration), Table 10: Schedule of Assessments (LAM-002A/Rituximab Combination Therapy), and Table 11: Schedule of Assessments (LAM-002A/Atezolizumab Combination Therapy) – in Section 8.7. During the extension stage (Stage 3), collection of clinical data by the sponsor will be limited to serious adverse event (SAE) reports. Study drug accountability will be managed per site procedures; relevant pharmacy records may be collected by the sponsor to document study drug disposition.

8.1. Screening/Baseline Evaluations Only

8.1.1. Informed Consent

Each potential subject must sign a written informed consent form (ICF) prior to performing any study-specific procedure. Principal investigators (PIs) at each site are responsible for maintaining a record of all subjects screened, including both those who enter the study and those who are excluded.

8.1.2. Inclusion and Exclusion Criteria

During Screening, inclusion and exclusion criteria will be reviewed for each potential subject and confirmed by Day 1 of Cycle 1.

8.1.3. Medical History

At Screening, a complete medical history will be obtained from each subject, including relevant medical history, current primary cancer diagnosis, pathology reports (including corresponding flow cytometry and cytogenetic reports), prior cancer treatments (chemo- and immunotherapies, radiation therapy, surgeries), and disease-specific characteristics, such as tumor stage and histology.

8.1.4. Demography

At Screening, subject demographic data will be collected, including date of birth, gender, race, and ethnicity.

8.1.5. Disease Status Assessment for Subjects with NHL

Pretreatment tumor assessments will be performed within 30 days of the first dose of study treatment and will include diagnostic CT scans (with intravenous contrast) or Positron Emission Tomography (PET)/Computerized Tomography Scans (CT scan) for patients with lymphoma, bone marrow aspirate/biopsy, complete blood counts and physical examination. It is anticipated that in most cases the PET/CT scans will be conducted using a single instrument, i.e., as a PET/CT scan (CT scans should be performed using a contiguous reconstruction algorithm of ≤ 5 mm). However, MRI is an acceptable alternative method for assessing disease in subjects

Clinical Study Report 16.1 Study Information Protocol: LAM-002A-NHL-CLN01

Version 9, 18 Feb 2020

who cannot receive intravenous contrast with CT scans. In such subjects MRI and PET scans will have to be obtained separately.

Suitable scans performed prior to screening and within 30 days before first dose may be used for baseline tumor assessments. Similarly bone marrow biopsies/aspirates performed within 2 months prior to first dose may be used for baseline assessments. For subjects with NHL, baseline bone marrow biopsies/aspirates may be omitted if not deemed essential for response assessment or patient management and there is another source of tumor tissue for pretreatment evaluation of gene expression and prognosis. For subjects with CLL/SLL, a baseline bone marrow aspirate is required unless the presence of sufficient circulating cells in the peripheral blood (e.g., $ALC \ge 10 \times 10^9/L$) permits assessment of baseline parameters for gene expression and prognosis. Details of assessments will be collected on the eCRF and must be filed in the subject's medical record.

Fresh tumor tissue (preferred) or archival tumor tissue that was obtained within 4 months prior to the start of screening (provided adequate quantities are available) must be obtained pretreatment for nucleic acid extraction. For subjects undergoing a biopsy, adequate tumor tissue should be acquired via excisional biopsy, incisional biopsy or core needle biopsy (e.g., ≥ 3 passes using a 16-gauge core needle). Confirmation of tumor in biopsy with fine needle aspirate, touch prep, or FFPE processing is requested when possible. The tumor lesion selected should not have been previously irradiated and should not be an index lesion that is followed for response assessment. Alternatively, cells from a bone marrow aspirate may be obtained in subjects with bone marrow involvement due to NHL ($\geq 50\%$ of cells). Tissue will be submitted for evaluation of the percentage of tumor cells and analysis of genetic alterations and/or gene expression that may predict anti-lymphoma activity and/or pharmacodynamics activity.

In addition, tumor tissue from the fresh biopsy or most recently availably biopsy or surgery will be evaluated for known prognostic characteristics (e.g., for DLBCL: ABC or GCB subtype; expression of BCL2, BCL6, Ki-67, CD20, and MYC; other mutational status), for PDL1 status, and for immune infiltration. The baseline biopsy procedure (if required) should ideally be performed after the study candidate has undergone the baseline radiology examination and is otherwise considered eligible for study participation.

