7. SELECTION OF SUBJECTS

7.1. Subject Inclusion Criteria

- 1. The subject is capable of understanding and complying with the protocol requirements and has signed the informed consent document. The subject is able to provide signed and dated informed consent prior to initiation of any study-specific procedures.
- 2. Subjects must have a histologically confirmed diagnosis of B-cell NHL limited to FL, DLBCL, MCL, MZL, primary mediastinal B-cell lymphoma (PMBL), or CLL/SLL according to the World Health Organization (WHO) classification, that has progressed and for which standard curative measures do not exist or are no longer effective.
- 3. Subjects with DLBCL must have progressed after transplant, or be unwilling, unable or not an appropriate candidate for an autologous stem cell or bone marrow transplant.
- 4. Subjects must have radiographically measurable lymphadenopathy or extranodal lymphoid malignancy (defined as the presence of ≥ 1 lesion that measures ≥ 2.0 cm in the longest dimension [LD] and ≥ 1.0 cm in the longest perpendicular dimension [LPD] as assessed radiographically).
- 5. The subject is ≥ 18 years old.
- 6. The subject has an Eastern Cooperative Oncology Group (ECOG) Performance Status of ≤ 2.
- 7. The subject has organ and marrow function as follows:
 - a. Absolute neutrophil count (ANC) $\geq 1.0 \times 10^9/L$ (1,000/mm³) without hematopoietic-stimulating factor support
 - b. Platelets $> 50 \times 10^9 / L (50,000 / mm^3)$
 - c. Total bilirubin ≤ 1.5 x the upper limit of normal (ULN) except for subjects with known Gilbert disease (total bilirubin ≤ 3 x ULN permitted)
 - d. Serum creatinine ≤ 1.5 x ULN or calculated creatinine clearance ≥ 60 mL/min (based on the Cockcroft-Gault formula)
 - e. Alanine aminotransferase (ALT) and aspartate aminotransferase (AST) \leq 2.5 x ULN if no liver involvement, or \leq 5 x ULN with liver involvement
 - f. Albumin $\geq 2 \text{ g/dL}$
 - g. Note: Grade ≥ 3 neutropenia or thrombocytopenia is permitted if the abnormality is related to bone marrow involvement with hematological malignancy (as documented by bone marrow biopsy/aspirate obtained since the last prior therapy).
- 8. The subject has the ability to swallow oral capsules without difficulty.

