7.2. Subject Exclusion Criteria

- 1. Subjects with central nervous system (CNS) lymphoma are not eligible for the trial unless the disease had been treated and the subject remained asymptomatic (for at least 6 months) with no active CNS lymphoma, as determined by lumbar puncture, computed tomography scan (CT), or magnetic resonance imaging (MRI).
- 2. The subject has received cytotoxic chemotherapy (including investigational cytotoxic chemotherapy) within 3 weeks, or nitrosoureas/ mitomycin C within 6 weeks before the first dose of study treatment.
- 3. The subject has received treatment with a therapeutic antibody less than 4 weeks before the first dose of study treatment. For subjects with rapidly progressive or aggressive subtypes of lymphoma, a minimum period of 2 weeks between the last treatment with a therapeutic antibody and the first dose of study treatment may be permitted following discussion with the medical monitor.
- 4. The subject has received radioimmunotherapy within 6 weeks of the first dose of study treatment.
- 5. The subject has received radiation therapy within 14 days of the first dose of study treatment.
- 6. The subject has received prior treatment with a small-molecule kinase inhibitor or other small-molecule investigational agent within 14 days or 5 half-lives of the compound or active metabolites, whichever is greater, before the first dose of study treatment.
- 7. Stage 2 (study candidates being considered for LAM-002A/rituximab combination therapy): Best overall response with the last regimen containing an anti-CD20 antibody (eg, rituximab, ofatumumab, obinutuzumab) was disease progression.

Clinical Study Report 16.1 Study Information

Protocol: LAM-002A-NHL-CLN01

Version 9, 18 Feb 2020

- 8. Stage 2 (study candidates being considered for LAM-002A/atezolizumab combination therapy): Prior exposure to a CD137 agonist or an immune checkpoint inhibitor, including an anti-PD1, anti-PDL1, or anti-CTLA4 therapeutic antibody.
- 9. Stage 2 (study candidates being considered for LAM-002A/atezolizumab combination therapy): treatment with a live, attenuated vaccine within 4 weeks prior to initiation of study treatment, or anticipation of need for such a vaccine during atezolizumab treatment or within 5 months after the last dose of atezolizumab.
- 10. Stage 2 (study candidates being considered for LAM-002A/atezolizumab combination therapy): Current treatment with anti-viral therapy for hepatitis B virus (HBV).

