1.5. Definitions of Tumor Response and Progression

Responses will be categorized as complete response (CR), partial response (PR), stable disease (SD), or progressive disease (PD). In addition, a response category of nonevaluable (NE) is provided for situations in which there is inadequate information to otherwise categorize response status.

The best overall response will be determined. The best overall response is the best on-treatment response from baseline recorded from the start of treatment until PD/recurrence. The baseline measurement will be taken as a reference for determinations of response. The nadir measurement will be taken as a reference for PD; this measurement constitutes the smallest measurement recorded, including the baseline measurement if this is the smallest measurement. For FDG-avid tumors, metabolic criteria for response by PET-CT will take precedence over anatomic criteria for response by contrast CT when assessing CR.

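### The 30-day baseline-scan window is longer than most prior-therapy washouts, and nothing requires the scan to follow the last prior therapy, so carry-over shrinkage can count as response

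*Combined protocol and SAP*

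**What the plan says.** On baseline imaging, Section 8.1.5 states: "Suitable scans performed prior to screening and within 30 days before first dose may be used for baseline tumor assessments". The imaging footnotes of Tables 8 to 11 repeat the rule, and Section 11 gives the same 30-day window. What makes a scan suitable is not defined.

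On prior therapy, Section 7.2 excludes a candidate under these conditions:

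- Cytotoxics: "The subject has received cytotoxic chemotherapy (including investigational cytotoxic chemotherapy) within 3 weeks, or nitrosoureas/ mitomycin C within 6 weeks before the first dose".
- Antibodies: "The subject has received treatment with a therapeutic antibody less than 4 weeks before the first dose of study treatment". For rapidly progressive or aggressive subtypes, after discussion with the medical monitor, "a minimum period of 2 weeks between the last treatment with a therapeutic antibody and the first dose of study treatment may be permitted".
- Radiotherapy: "The subject has received radiation therapy within 14 days of the first dose of study treatment".
- Small molecules: 14 days or 5 half-lives, whichever is greater.
- Radioimmunotherapy: 6 weeks.

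On response, Appendix 2, Section 1.5 says: "The baseline measurement will be taken as a reference for determinations of response". Section 1.5.2 sets partial response at an SPD reduction of at least 50% from that baseline. Neither section asks for a confirming scan.

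A condition tying an assessment to the end of prior treatment appears once, for the cytopenia allowance in Section 7.1, where marrow involvement must be shown "as documented by bone marrow biopsy/aspirate obtained since the last prior therapy". It is not applied to imaging.

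**The concern.** A baseline scan for a single-arm response rate should describe the disease as it stands when study treatment starts. Here the scan may be older than the last course of other anticancer treatment. If that treatment shrinks the tumour after the scan, the reduction is measured against the older and larger SPD and is credited to LAM-002A. There is no control arm against which to separate the two effects.

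The read-out most exposed is the FL accrual boundary in Section 14.1.2, where a single response can decide whether the lower confidence bound clears 20%. The six-subject cohorts are exposed too: one such response would remove the 0/6 result that Section 14.1.2 uses to exclude an ORR of 35% or more.

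**Working it through.** **1. Date arithmetic.** Largest possible overlap = 30 days minus the minimum washout in Section 7.2.

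| Prior therapy | Minimum washout (days) | Overlap (days) |
|---|---|---|
| Radiotherapy | 14 | 30 − 14 = 16 |
| Small molecules, short half-life | 14 | 30 − 14 = 16 |
| Cytotoxics | 21 | 30 − 21 = 9 |
| Antibodies, standard | 28 | 30 − 28 = 2 |
| Antibodies, exception | 14 | 30 − 14 = 16 |
| Nitrosoureas, mitomycin C | 42 | none |
| Radioimmunotherapy | 42 | none |

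For small molecules the overlap vanishes once 5 half-lives reach 30 days, that is, at a half-life of 6 days or more. Four of the six classes (not counting the antibody exception separately) have a washout shorter than the scan window.

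If the scan is taken inside the Day -28 to -1 screening window instead, the overlaps become 28 − 14 = 14, 28 − 21 = 7 and 28 − 28 = 0.

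**2. The plan's own figures.** The exact 1-sided 95% lower bound at 8/20 is 0.217, which agrees with the plan's claim of at least 20%. At a true ORR of 20%, P(X ≥ 8 of 20) = 0.032. The upper bound for 0/6 is 1 − 0.1^(1/6) = 0.319, which agrees with the stated 32%.

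**3. Effect on the FL monotherapy boundary.** Assume that a fraction f of subjects reach a 50% SPD reduction through carry-over alone and that the true ORR is 20%. Then observed ORR = 0.20 + 0.80 × f. The crossing probability comes from an exact recursion over the n/N pairs in Section 14.1.2, stopping at the first crossing. Two values are listed at N = 11; 6 is used here.

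| f (assumed) | Observed ORR | P(cross boundary) |
|---|---|---|
| 0 | 0.200 | 0.081 |
| 1% | 0.208 | 0.094 |
| 2% | 0.216 | 0.109 |
| 5% | 0.240 | 0.161 |
| 10% | 0.280 | 0.272 |

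Using 5/11 instead gives 0.087, 0.170 and 0.283 at f = 0, 5% and 10%, so the pattern does not depend on that choice. The 0.081 at f = 0 reflects repeated looks and has nothing to do with carry-over; only the increase above it matters here.

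**4. One misattributed response.** If one of the 8 responders at 8/20 owed the response to carry-over, the count attributable to LAM-002A is 7/20. Its lower bound is 0.177, below the 20% to be excluded.

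**The case against.** The strongest reply is that the sequence is unlikely. Section 7.1 requires disease that has progressed, and Section 6.1.2 describes the expansion cohorts as having progressive disease. A subject who is shrinking quickly from a recent treatment fits that description poorly. Eligibility forms are reviewed centrally (Section 6.4), and allocation considers therapy history and current disease status (Section 6.1.4). Appendix 2, Section 1.3 places baseline imaging in the screening period, which removes the 2-day standard antibody overlap. Previously irradiated lesions may be classed as non-index, and up to six index lesions are ideally spread over different regions, so local radiotherapy would seldom halve the total SPD. All of this lowers the risk. None of it closes the gap: progression need not be shown on a scan after the last therapy, the non-index wording is optional and covers radiation only, and in-window scans still leave overlaps of 14 and 7 days.

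Second, a reader might infer that the rule biases ORR upward overall. The documents do not support that. Carry-over alone inflates ORR, but an early scan in growing lymphoma also misses growth before first dose, which makes a 50% reduction harder to reach. The net direction is not established.

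Third, on-study scans repeat at Cycles 3, 5 and 7, and Section 4.1.4.2 reports several responses lasting over 12 months. That fits poorly with transient carry-over in those subjects. It does not protect ORR, which rests on best overall response.

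Fourth, the marrow condition in Section 7.1 serves to establish the cause of a cytopenia. It shows that the protocol can express such a condition; it does not show that the imaging rule contradicts it.

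**Conclusion.** The gap is real and follows from the text: a baseline scan may predate the last prior therapy by up to 16 days (radiotherapy, short-half-life small molecules), 9 days (cytotoxics) or 2 days (standard antibody washout). The 16-day antibody overlap exists only under the exception for rapidly progressive or aggressive subtypes, so it should not be read as applying to typical FL.

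The size of the effect is unknown. Each f in the table is an assumption, and 5% or 10% should not be read as an estimate. At 1% to 2% the boundary-crossing probability rises only from 0.081 to between 0.094 and 0.109. The firmer statement is that one misattributed response at 8/20 is enough to take the lower bound below 20%.

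Two further inferences are not supported. The documents do not show that any subject followed this sequence. And 0/6 is not a stopping rule: Section 14.1.2 says only that an ORR of 35% or more can then be excluded, so one carry-over response would remove that statement without reversing a mandated stop. Likewise, crossing the FL boundary means that accrual can be considered sufficient, in a study where activity is a preliminary, secondary objective.

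This is a worthwhile, inexpensive improvement, and it does not invalidate the efficacy read-out.

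**What to change.** In the SAP, flag every subject whose baseline scan date precedes the date of the last prior anticancer therapy, including radiotherapy. Report ORR and boundary status twice: with those subjects' responses counted and with them not counted. Section 8.1.3 lists prior treatments without mentioning dates, but the dates are needed anyway to check the washouts in Section 7.2. This is the main part of the fix, because Version 9 was written as the study moved toward its extension stage.

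For any further enrolment, state in Section 8.1.5, Section 11 and the imaging footnotes of Tables 8 to 11 that the baseline scan must fall within 30 days before first dose and after the last prior anticancer therapy. The possible overlap then becomes zero. The washout periods stay as they are.

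The cost is one sensitivity line and, if enrolment continues, an occasional repeat scan.

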8.1.6. Disease Status Assessments for Subjects with CLL/SLL

All subjects with CLL must have baseline imaging (with CT scans [preferred] or MRI scans).

Subjects with CLL/SLL must provide either a fresh blood sample containing circulating tumor cells or a bone marrow aspirate sample pretreatment. Tissue will be submitted for evaluation of the percentage of tumor cells and analysis of genetic alterations and/or gene expression that may predict anticancer activity and/or pharmacodynamic activity. In addition, for subjects with CLL/SLL, the sponsor may arrange for a portion of the sample to be evaluated at a sponsor-specified laboratory for known prognostic markers (e.g., quantitative immunoglobulins, FISH panel [chromosome 11q deletion, 13q deletion, 17p deletion and 12 trisomy], DNA mutational analysis for p53, IgHV [including IgHV3-21], and other genes of interest in CLL [e.g., Notch]; flow cytometry [for CD5, CD10, CD11c, CD19, CD20, CD23, CD38, CD45, kappa and lambda light chains and ZAP-70], and/or β2-microglobulin). The baseline bone marrow aspiration procedure (if required) should ideally be performed after the study candidate has undergone the baseline radiology examination and is otherwise considered eligible for study participation.

Version 9, 18 Feb 2020

8.2. Baseline Assessment for All Subjects

8.2.1. Physical Examination and ECOG Performance Status

Complete physical examination (PE) will be performed at Screening and may include evaluation of head, ears, eyes, nose, and throat, dermatological, respiratory, cardiovascular, gastrointestinal, endocrine/metabolic, neurological, lymphatic, and musculoskeletal systems. A directed PE, including weight, will be performed within 72 hours prior to the start of each cycle and at End of Treatment.

ECOG Performance Status will be assessed at the same time points as PEs (See Appendix 1).

8.2.2. Pregnancy Test

Serum or urine pregnancy test will be performed for WCBP at Screening, within 72 hours of Day 1 of each treatment cycle, and at the EOT visits. The test does not need to be repeated at Cycle 1 Day 1 if baseline testing was performed within 72 hours of first dose. However, the result must be negative for the subject to be enrolled in the study and to continue participation.

8.2.3. Urinalysis

A urine sample will be obtained at Screening, within 72 hours of Day 1 of each treatment cycle, and at the EOT visit. Analysis will include assessment of appearance, specific gravity and pH as well as a semi-quantitative "dipstick" evaluation of glucose, protein, bilirubin, ketones, leukocytes and blood. Microscopic examination of sediment will be performed if urinalysis is positive for white blood cells (WBCs), proteins, or blood.

8.2.4. Electrocardiogram

A 12-lead ECG with subject resting for 5 minutes will be done at Screening. Additional ECGs will be conducted according to Table 8: Schedule of Assessments (LAM-002A Continuous Monotherapy Administration), Table 9: Schedule of Assessments (LAM-002A Intermittent Monotherapy Administration), Table 10: Schedule of Assessments (LAM-002A/Rituximab Combination Therapy), and Table 11: Schedule of Assessments (LAM-002A/Atezolizumab Combination Therapy) – in Section 8.7 and more often if clinically indicated. Parameters measured will include heart rate, PR, QRS, QT, and QTc intervals (calculated by the Fridericia correction formula. Bazett's correction is acceptable if institutional policy). See Section 12 for PK time points. The ECGs will be reviewed and signed by the investigator.

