4.1.4.3. Safety

Apilimod dimesylate has been generally well tolerated in humans. In patient populations with Crohn's disease or psoriasis, more frequent (> 10%) AEs experienced to date included headache, upper respiratory tract infection, and nausea; less frequent (> 5% to 10%) AEs included dizziness, fatigue, and nasopharyngitis; and rare (2% to 5%) AEs included diarrhea, arthralgia, fever, abdominal pain, peripheral edema, and vomiting. In general, most AEs were assessed as mild in severity.

In the ongoing trial of LAM-002A in patients with hematological cancers, dose-dependent gastrointestinal events of nausea, vomiting, and diarrhea have been observed. One patient with DLBCL developed acute transient elevations in serum creatinine and blood-urea nitrogen (BUN) due to tumor lysis syndrome (TLS) shortly after starting LAM-002A at a dose of 125 mg BID. One patient with a hematological malignancy receiving the drug at 150 mg BID developed asymptomatic Grade 3 hyponatremia that was attributed to the combined effects of LAM-002A-induced diarrhea and hydrochlorothiazide administration. No other clinically significant safety signals in laboratory, physical examination, or vital sign findings have been noted.

Cardiac monitoring in clinical studies to date has not revealed any major issues. However, in a thorough QT/QTc study, apilimod dimesylate at doses of 50 mg and 150 mg was associated with repolarization findings in excess of those deemed negative by International Conference on Harmonisation (ICH) E14 guidance. The magnitude of the change was modest (\sim 8.5 msec) and the root-mean-square based analyses did not demonstrate as large an increase in cardiac repolarization time (\leq 1.22 msec) as that identified using the Fridericia method. Therefore, the significance of this finding is unclear. Preliminary QTc observations in the ongoing study in patients with hematological malignancies suggest the potential for dose- and exposure-dependent Grade 1 or 2 QT prolongation.

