6.9.7. Drugs Known to Prolong the OT Interval

In a thorough QTc study, apilimod dimesylate at doses of 50 mg and 150 mg was associated with repolarization findings in excess of those deemed negative by regulatory guidance. The magnitude of the change was modest (~8.5 msec), peaked at 4 hours and did not demonstrate a dose trend. Preliminary QTc observations in the ongoing study in patients with hematological malignancies suggest the potential for dose- and exposure dependent Grade 1 or 2 QT prolongation.

As a precaution, the clinical potential of LAM-002A to prolong the QT interval will be assessed in this study. Accordingly, co-administration of LAM-002A and known QT-prolonging drugs is to be minimized because use of such drugs might confound interpretation of QT data from the trial.

Based on these considerations, protocol candidates who require therapy with drugs known to prolong the QT interval (as listed in Table 16) should not be enrolled into the study. If medically justified, protocol candidates may be enrolled if such drugs can be discontinued or alternative drugs that do not affect QT can be substituted >7 days before the first dose of study drug.

After the subject is enrolled to the protocol, use of drugs known to prolong the QT interval should be minimized but is not prohibited if administration of such drug is necessary and the subject appears to be benefiting from protocol therapy.

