- 17. Stage 2 (study candidates being considered for LAM-002A/atezolizumab combination therapy): Active or history of autoimmune disease or immune deficiency, including, but not limited to, myasthenia gravis, myositis, autoimmune hepatitis, systemic lupus erythematosus, rheumatoid arthritis, inflammatory bowel disease, antiphospholipid

Version 9, 18 Feb 2020

antibody syndrome, Wegener granulomatosis, Sjögren syndrome, Guillain-Barré syndrome, or multiple sclerosis (with the following exceptions: history of autoimmune-related hypothyroidism and receiving thyroid-replacement hormone; controlled Type 1 diabetes mellitus on an insulin regimen; eczema, psoriasis, lichen simplex chronicus, or vitiligo with dermatologic manifestations if rash covers < 10% of body surface area, disease is well controlled at baseline and requires only low-potency topical corticosteroids, there is no occurrence of acute exacerbations of the underlying condition requiring psoralen plus ultraviolet A radiation, methotrexate, retinoids, biologic agents, oral calcineurin inhibitors, or high-potency or oral corticosteroids within the previous 12 months, and the subject does not have extra-cutaneous disease [e.g., psoriatic arthritis]).

- 18. The subject has a history of malabsorption or other GI disease that may significantly alter the absorption of apilimod (e.g., \geq Grade 2 nausea, vomiting or diarrhea).
- 19. The subject has undergone major surgery within 28 days prior to first dose of study drug.
- 20. The subject has a QTcF > 470 msec on screening ECG or has a history or risk factors for, or use of medications known to prolong QTc interval or that may be associated with Torsades de Pointes within 7 days of treatment start.
- 21. The subject has past history of tuberculosis (TB) or active infection with TB, human immunodeficiency virus (HIV), hepatitis B virus (HBV) or hepatitis C virus (HCV). Note: Subjects must have negative human immunodeficiency virus (HIV) antibody, negative hepatitis B surface antigen (HBsAg) and negative hepatitis B core (HBc) antibody or undetectable HBV deoxyribonucleic acid (DNA) by quantitative polymerase chain reaction (PCR) testing, and negative HCV antibody or negative HCV ribonucleic acid (RNA) by quantitative PCR.
- 22. The subject is lactating and breast feeding.
- 23. The subject has a previously identified allergy or hypersensitivity to components of the study treatment formulation.

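### Sites may report QTc by Fridericia or Bazett and no rule requires one correction, so absolute QTc summaries, grades and outlier counts can mix scales by site

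*Combined protocol and SAP*

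**What the plan says.** Section 8.2.4 lists what each ECG yields: "Parameters measured will include heart rate, PR, QRS, QT, and QTc intervals". The QTc is to be "calculated by the Fridericia correction formula. Bazett's correction is acceptable if institutional policy". On reading, it adds only that "The ECGs will be reviewed and signed by the investigator"; no central reading is described.

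Elsewhere the QT material is on Fridericia. Exclusion 20 (Section 7.2, repeated in the synopsis) applies when "The subject has a QTcF > 470 msec on screening ECG". Section 6.9.7 says of the thorough QTc study: "The magnitude of the change was modest (~8.5 msec), peaked at 4 hours and did not demonstrate a dose trend". Section 4.1.4.3 shows that this figure is a Fridericia result, because it contrasts a root-mean-square analysis (at most 1.22 msec) with the increase "as that identified using the Fridericia method".

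QT is a declared question of the trial: "the clinical potential of LAM-002A to prolong the QT interval will be assessed in this study". Both sections also report preliminary signs, in this trial's own patients, of low-grade QT prolongation that rises with dose and exposure.

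For analysis, Section 14.7 lists ECG changes among the safety summaries, and the synopsis says that cardiac intervals will be reported. Neither names a correction formula. Section 14.2 leaves detailed methods to an SAP and has results summarised by dose cohort.

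**The concern.** The two corrections use different powers of the RR interval, so they agree only at 60 bpm and move apart as heart rate departs from it. If some sites follow an institutional Bazett policy, the QTc column of the database holds two different quantities, sorted by site and not by dose. Three uses are exposed.

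- **Absolute values and threshold counts.** A mean, a maximum or a count above a cut-off would depend partly on which sites contributed. Stage 1 cohorts have 3 to 6 subjects (Section 6.6), so one subject on the other scale can move a cohort mean noticeably.
- **Grades.** The suspected signal is described in grades, and a grade can change with the formula. Table 4 names no QTc threshold, but its general entry for non-hematologic toxicity of Grade 3 or higher means that a QTc grade could in principle bear on a DLT.
- **Eligibility.** The limit is stated as QTcF. A site that reads its routine Bazett value against 470 msec applies a different criterion.

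**Working it through.** **Inputs from the documents.** Prior effect about 8.5 msec, Fridericia (Sections 4.1.4.3 and 6.9.7); entry limit QTcF 470 msec (Section 7.2); QT and heart rate both recorded (Section 8.2.4). The 8.5 msec is an empirical result whose data are not given, so it cannot be reproduced and serves only as a yardstick.

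**Assumptions.** The documents give no heart rates or baseline QTc values. I take 50 to 100 bpm and QTcF 380 to 470 msec, with 420 msec as the central case.

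**Formulas.** With RR = 60/HR in seconds, QTcF = QT/RR^(1/3) and QTcB = QT/RR^(1/2). Hence

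QTcB - QTcF = QTcF × [(HR/60)^(1/6) - 1].

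**1. Gap on a single ECG (msec).**

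| HR (bpm) | QTcF 380 | QTcF 420 | QTcF 470 |
|---|---|---|---|
| 50 | -11.4 | -12.6 | -14.1 |
| 60 | 0.0 | 0.0 | 0.0 |
| 65 | 5.1 | 5.6 | 6.3 |
| 70 | 9.9 | 10.9 | 12.2 |
| 80 | 18.7 | 20.6 | 23.1 |
| 90 | 26.6 | 29.4 | 32.9 |
| 100 | 33.8 | 37.3 | 41.8 |

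The gap equals ±8.5 msec at HR = 60 × (1 ± 8.5/QTcF)^6. At QTcF 420 that is 67.7 and 53.1 bpm; over QTcF 380 to 470 it is 66.8 to 68.5 and 52.4 to 53.8 bpm. Between about 53 and 68 bpm the formulas differ by less than the prior effect.

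**2. Effect on an absolute mean.** The shift is the share of subjects on Bazett times the gap. At 80 bpm and QTcF 420, shares of 10%, 25% and 50% shift the mean by 2.1, 5.2 and 10.3 msec. One Bazett subject in a cohort of 3 shifts it by 20.6/3 = 6.9 msec; one in 6 by 20.6/6 = 3.4 msec.

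**3. Effect on change from baseline, same formula at both visits.** With heart rate unchanged, a true QTcF change of 8.5 msec reads 8.5 × (HR/60)^(1/6) on Bazett: 8.7 msec at 70 bpm and 9.1 at 90. The offset almost cancels. If heart rate moves from HR1 to HR2 with QTcF constant, Bazett adds QTcF × [(HR2/60)^(1/6) - (HR1/60)^(1/6)]. At QTcF 420:

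- 70 to 75 bpm adds 5.0 msec
- 70 to 80 bpm adds 9.7 msec
- 80 to 90 bpm adds 8.7 msec
- 80 to 70 bpm subtracts 9.7 msec

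The rise needed to add 8.5 msec is 7.7 bpm from 60, 8.7 from 70, 9.2 from 75 and 9.7 from 80.

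**4. Entry limit.** A Bazett value of 470 msec corresponds to QTcF 470/(HR/60)^(1/6): 484.5 msec at 50 bpm, 458.1 at 70, 448.0 at 80 and 439.3 at 90. For example, QT 400 msec at 90 bpm is 458 msec by Fridericia and 490 msec by Bazett, on opposite sides of the limit. Above 60 bpm, misuse excludes subjects whom the criterion admits; below 60 bpm it can admit subjects whom the criterion excludes.

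**The case against.** Much of the case on the other side stands.

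- A reader might infer that the two scales always differ by more than the drug's known effect. They do not: they agree at 60 bpm, and the gap is under 8.5 msec from about 53 to 68 bpm. No heart-rate data are given to say where subjects will lie. The yardstick itself is qualified, since Section 4.1.4.3 reports a much smaller root-mean-square result and calls the finding's significance unclear.
- The 8.5 msec is a change, and Section 14.7 plans ECG changes. If a site keeps one formula and heart rate is stable, the offset nearly cancels. The documents report no effect of the drug on heart rate, so they do not show that the change analysis is distorted.
- A reader might infer that the plan intends to pool both scales. It does not say so. Section 14.2 defers methods to an SAP, and the part of the document available here contains no SAP text. Uncorrected QT and heart rate are recorded, so nothing is lost.
- A reader might infer that a Bazett site cannot apply the entry limit. It can: exclusion 20 names QTcF, and the site has both inputs. Eligibility forms are also checked before dosing (Section 6.4).
- The primary endpoint is DLT frequency, and ECG results are secondary and descriptive. The protocol text does not itself specify outlier counts.

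What does not fall away is that Section 8.2.4 expressly permits a second scale and no later section of the protocol brings the values back to one. That leaves absolute values, grades and any threshold counts open to mixing. A later derivation in the SAP could harmonise the analysis but could not undo an enrolment decision already made on a Bazett value.

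**Conclusion.** The concern holds in a bounded form. The protocol allows the correction to vary by site policy, while its entry limit and its prior effect estimate are on Fridericia, and it gives no rule for using one correction. Absolute QTc summaries, grades and outlier counts can mix scales, by about 11 to 37 msec at 70 to 100 bpm and about -13 msec at 50 bpm, assuming QTcF 420 msec. Change from baseline is at risk mainly when heart rate shifts. Eligibility is at risk only if a site substitutes its Bazett value for the QTcF that the criterion names.

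The documents do not support the stronger readings: that the scales differ by more than 8.5 msec at every heart rate, that the change analysis will be distorted, or that the entry limit cannot be applied. The size of the problem in practice depends on heart rates and on the number of Bazett sites, and neither is given. This is a secondary safety-reporting matter worth correcting because the correction is free.

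**What to change.** State in Sections 8.2.4 and 14.7 that QTcF, derived from the recorded QT and heart rate for every ECG, is the only correction used in QTc summaries, in grading and in the existing QTcF eligibility check. Carry the same derivation into the SAP. Bazett values may stay in source records where institutional policy produces them, but are not analysed.

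The cost is one derived variable and a sentence in each section. No additional ECGs, visits or subjects are needed, and the 470 msec limit is unchanged. With the rule in place, the between-formula offset in the summaries is zero at every heart rate, and they sit on the same scale as the prior effect and the entry criterion.
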